7. If female and not infertile, must agree to use one of the following forms of contraception for the duration of study participation: systemic hormonal treatment, an IUD which was implanted at least 2 months prior to screening, or "double-barrier" contraception.	Physician evaluation
8. Willing/capacity to provide informed consent	Physician evaluation

Create or insert table to describe the exclusion criteria and methods to ascertain them

Criterion	Method of Ascertainment
-----------	-------------------------

- | | |
|--|--------------------------------------|
| 1. Substance dependence or abuse (excluding nicotine) in the past 90 days | Physician evaluation |
| 2. Current significant laboratory abnormality* | screening labs |
| 3. History of seizure, epilepsy in self or first degree relatives, stroke, brain surgery, head injury with loss of consciousness > 1 hour or clear cognitive sequelae, intracranial metal implants, known structural brain lesion, devices that may be affected by tDCS (pacemaker, medication pump, cochlear implant, implanted brain stimulator) | Physician evaluation/Medical history |
| 4. Frequent and persistent migraines | Physician evaluation/Medical history |
| 5. History of adverse reaction to neurostimulation or open skin wounds that would preclude safe placement of tDCS electrodes | Self report |
| 6. Participation in study of investigational medication/device within 4 weeks | Self report |
| 7. Current use of medications known to lower seizure threshold (Lithium, Theophylline, Tricyclic antidepressants, Bupropion >450 mg/day and Clozapine >600 mg/day, brand name and generic methylphenidate/mixed amphetamine salts) | Physician evaluation/Medical history |
| 8. If female, pregnant or breast feeding at the time of screening | Urine pregnancy test and self report |
| 9. For MRI study only: Claustrophobia or metal implants or paramagnetic objects contained within the body which may interfere with the MRI scan, as determined according to the guidelines set forth in the following reference book: "Guide to MR procedures and metallic objects" Sherlock, PhD, Lippincott-Raven press, NY 1998. | History, interview |

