*Note: Clinically significant laboratory abnormality refers to patient lab results that fall significantly outside the established ranges, may be indicative of the presence of a medical condition, and are not thought to reflect an artifact or routine lab error (e.g., hemolysis). Results of laboratory tests are reviewed by the study physician prior to any treatment. Abnormal lab results of clinical significance that cannot be resolved (e.g., by repeating the test to rule out laboratory error or poor quality of the original sample) will lead to exclusion from the study. Abnormal laboratory values associated with known, chronic, stable medical conditions will not be considered exclusionary unless the condition would increase risk of study participation.

Inclusion/Exclusion Criteria #2

Name the subject group/sub sample

Schizophrenia patients without auditory hallucinations

Create or insert table to describe the inclusion criteria and methods to ascertain them

Criterion	Method of Ascertainment
1. Age between 18-55	Self report
2. SCID primary diagnosis of DSM-IV schizophrenia or schizoaffective	SCID
3. Right handed	Edinburgh Handedness Questionnaire
4. Normal hearing	Physician evaluation
5. Stable course of antipsychotic medication for >1 month	Physician evaluation/Psychiatric history
6. Use of effective method of birth control for women of childbearing capacity	Physician evaluation
7. Willing/capacity to provide informed consent	Physician evaluation
8. Signed HIPAA authorization	Physician evaluation

Create or insert table to describe the exclusion criteria and methods to ascertain them

Criteria	Method of Ascertainment
1. Current persistent auditory verbal hallucinations	Auditory Hallucinations Rating Scale mean item score >0
2. Current or past history of substance dependence (excluding nicotine)	Physician evaluation
3. Substance abuse (excluding nicotine) within last 90 days	Physician evaluation/Urine toxicology screen
4. Current diagnosis of any other Axis I disorder	SCID/Psychiatric history
5. History of seizure, epilepsy in self or first degree relatives, stroke, brain surgery, head injury, intracranial metal implants, known structural brain lesion, devices that may be affected by tDCS (pacemaker, medication pump, cochlear implant, implanted brain stimulator)	Physician evaluation/Medical history

6. Frequent and persistent migraines	Physician evaluation/Medical history

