An M.D. who is unaffiliated but familiar with the study will ask potential participants who have been diagnosed with schizophrenia questions about the study procedures and associated risks in order to determine whether the patient understands the study and has the capacity to provide consent.

Study Procedures

Describe the procedures required for this study

Overview

AH + Sample

The treatment portion of this study will follow a double-blind parallel arm design in which patients, raters and investigators will be blinded with respect to condition assignment. All personnel will have undergone HIPAA and CITI training. Following a clinical evaluation to determine eligibility, patients will be assigned to either the active or the sham condition. In the active condition, patients will receive cathodal stimulation to the left temporo-parietal junction and anodal stimulation to the left dorsolateral prefrontal cortex at 2mA X 20 min in each session. In the sham condition, electrodes will be placed over the same regions, but current will be applied under a “sham” approach in which currents are initially ramped up over 30 s as in the active condition, but then immediately ramped down. Prior experience has shown that subjects do not distinguish the active and sham conditions. Patients will participate in two daily sessions of 20 minutes each for 5 consecutive weekdays. Auditory hallucinations as determined by the Auditory Hallucinations Rating Scale (AHRS) and the five dimensions of schizophrenia symptoms assessed in the Positive and Negative Syndrome Scale (PANSS) will be assessed at baseline, immediately following the final treatment, and at 1- and 3-month follow-up timepoints. AHRS will be repeated prior to first treatment session. All subjects will be assessed prior to and following initiation of 5-d treatment period using a neurophysiological battery sensitive to auditory dysfunction in schizophrenia, and neuropsychological tests of auditory and general neurocognitive impairment. The neurophysiological impact of tDCS will be assessed by MRI procedures described below at baseline and immediately following the final treatment. MRI sessions are optional for AVH+ patients.

Comparison Samples

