Subjects who consent for the optional MRI component will undergo MRI scanning, which includes structural 3-Tesla MRI scans and task-based fMRI scans and may include resting-state fMRI, resting-state ASL, magnetic resonance spectroscopy, and diffusion tensor imaging. None of the imaging modalities used in the study will include exogenous contrasts. Total scanning time will typically be around 2 hours and will not exceed 3 hours.

MRI scans will be performed immediately before and after the treatment period with active or sham tDCS in AVH+ patients. Comparison AVH- patients and healthy participants will also undergo MRI scanning despite not receiving tDCS. On the day of MRI scanning, subjects will be accompanied to the MRI suite at the NYSPI or Neurological Institute (depending on availability). The subject will be placed in a supine position on the camera table. Head will be positioned and a plastic head-holder will be used to decrease head movement during the scan. A bite bar (a soft but firm mouthpiece) will also be offered to the subjects to prevent excessive movement. Participants may or may not bite down on the bite bar. A new disposable cover for the bite bar will be used for every new participant. The participants will be given foam earplugs to reduce the noise of the MRI as well as a MRI-compatible hand held response pad for responding to the task (multi-button response units or mouse or a similar device). The tasks will be projected from an Insight liquid crystal display (LCD) projector zoomed to a screen inside the MR suite or viewed through dual channel binocular goggles (Silent Vision SV-2600; Avotec, Inc.). All subjects will undergo a structural MRI scan at the beginning of the session to allow for anatomical co-registration. Women will have urine pregnancy testing on each MRI scan day.

MRI Screening

Before inclusion in the MRI experiment, all subjects will be screened to ensure their eligibility for MRI scanning. The screening questionnaire includes questions regarding inclusion/exclusion criteria, including the presence of ferromagnetic implants, pubertal status, and pregnancy. Questions will be asked to determine if girls/women are post-menarche or pre-menopausal. Menarche will be defined as the onset of

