Although our MRI Scans are for research purposes (and not clinical purposes), a credentialed, board-certified radiologist will perform a clinical reading for gross structural abnormalities on every MRI within 1 month of scanning. If anything clinically significant is found, [name] will be notified immediately, and an appropriate clinical referral will be provided to the participant. In the case that an MRI technician or other member of the research team suspects that an MRI scan suggests evidence of a significant lesion, the PI will be notified immediately. If the reading yields a finding of immediate clinical concern, the radiologist will provide an oral report followed by a written note to the PI and Director of the MRI unit. A written report will be provided within two weeks of the oral report. Results of the MRI will be provided to the volunteers by a study physician. Volunteers can opt to receive a letter regarding the results of the MRI on the consent forms. Participants requesting a letter will receive one using the language provided by the IRB.

Treatment

Only patients in the AH+ sample will receive tDCS treatment. Prior to the first treatment, all female subjects will receive a pregnancy test. Stimulation will be performed using a battery-driven BrainStim SYS (Brainvision LLC, Germany), and transferred through two 7x5 cm sponge electrodes soaked in a saline solution (0.9% NaCl). In accordance with a recent tDCS study (21) showing beneficial effects of tDCS stimulation in reducing AVH in hallucinating schizophrenia patients, we will use a similar stimulation

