montage. In the active tDCS condition the cathodal electrode will be placed over the left temporoparietal junction, and the anodal electrode will be placed over right DLPFC. In accordance with recent studies of tDCS in other psychiatric or neurological illnesses(22-24), the stimulation level will be set at 2 mA for 20 minutes. Stimulation sessions will be conducted twice a day on 5 consecutive weekdays. Each daily session will be separated by at least 3 hours. In sham stimulation, electrodes are located in the same positions as in active stimulation and the same fade in/fade out ramp will be applied and the constant current will last only 30 s. Small current pulses will also occur infrequently (every 550 ms, 110 mA over 15 ms) through the remainder of the 20-minute session to produce similar stimulation sensation between conditions. During the treatment sessions, subjects will be allowed to watch a silent movie or read material of their choice.

Treatments will be administered by a trained, BA-level research assistant under supervision of an MD. The RA will undergo a progression of graduating steps consisting of observation, implementation under supervision, and implementation with guidance.

Safety:

We will monitor for potential adverse events of tDCS with the Wong-Baker Faces Pain Rating Scale (WBFPRS, Figure). The WBFPRS is readily understood by patients and provides general evaluation of discomfort. Additionally, we will monitor discomfort and potential objective adverse effects of tDCS (e.g. skin redness) as suggested by "Brunoni AR, Amadera J, Berbel B, Volz MS, Rizzerio BG, Fregni F. A systematic review on reporting and assessment of adverse effects associated with transcranial direct current stimulation. *Int J Neuropsychopharmacol.* 2011;14:1133-45: (Figure 2). Any score rated at a 3 or greater in severity will require immediate evaluation by a qualified member of the clinical team ([name]). Both are familiar with Brain stimulation procedures.

In these cases, the psychiatrist will check in via phone with the subject the following day, and then as clinically indicated.

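### For AH+ patients who opt into MRI, the baseline scan need not be read before tDCS starts, so an on-time clinical read can come after the whole course

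*Protocol*

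**What the plan says.** All of this is in the Protocol. The overview of the AH+ sample under Study Procedures places imaging at baseline and after the final treatment, and says that "MRI sessions are optional for AVH+ patients". The Magnetic Resonance Imaging section is more specific about timing: "MRI scans will be performed immediately before and after the treatment period with active or sham tDCS in AVH+ patients". The paragraph on clinical reading, which follows the fMRI task description, states that the scans serve research and that a board-certified radiologist "will perform a clinical reading for gross structural abnormalities on every MRI within 1 month of scanning". No shorter limit is set for the pre-treatment scan. The same paragraph requires the PI to be told at once if a technician or team member suspects a significant lesion.

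The Treatment section sets the length of the course: "Stimulation sessions will be conducted twice a day on 5 consecutive weekdays". The Lay Summary describes one 20-minute treatment a day, but also over five days, so the calendar is the same.

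Exclusion criterion 3 for the AH+ sample includes a "known structural brain lesion", ascertained by physician evaluation and medical history. For laboratory work the order is explicit: "Results of laboratory tests are reviewed by the study physician prior to any treatment". On assignment, the overview says: "Following a clinical evaluation to determine eligibility, patients will be assigned to either the active or the sham condition".

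**The concern.** The protocol treats a structural brain lesion, once known, as a reason not to give tDCS. For patients in the MRI component it also acquires a structural scan just before treatment and commits a radiologist to reading it for gross abnormalities. The two provisions are not joined up: the read may take up to a month, while the blinded course is over within about a week. Information that would have excluded the patient can therefore arrive, fully on time, after the blinded stimulation it should have prevented.

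What is at stake is the safety of individual patients in a volunteer subset. No efficacy estimate depends on it, and the rmMANCOVA in the SAP is untouched.

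**Working it through.** The protocol states no figure for the interval between the last session and the read, so there is none to reproduce. The check is calendar arithmetic.

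**Inputs**
- Read window W: one month after scanning (clinical reading paragraph). Taken as 28 to 31 days, since the protocol does not define it in days.
- Course span S, first to last session: five consecutive weekdays (Treatment). This is 4 calendar days for Monday to Friday, or 6 if the course crosses a weekend.
- Gap g from baseline scan to first session: no day count is given. The Magnetic Resonance Imaging section points to a short gap, so 0 to 3 days is assumed. The overview says only that imaging is at baseline, which could be a separate earlier visit, so longer gaps are also shown.

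**Formula**

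Days from last session to read deadline = W − g − S. The smallest value uses W = 28 and S = 6; the largest uses W = 31 and S = 4.

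| Gap g (days, assumed) | Smallest: 28 − g − 6 | Largest: 31 − g − 4 |
|---|---|---|
| 0 | 22 | 27 |
| 3 | 19 | 24 |
| 5 | 17 | 22 |
| 14 | 8 | 13 |

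Across gaps of 0 to 3 days the range is 19 to 27 days. Enumerating every weekday start date from 2013 to 2016 with a calendar-month deadline gives the same limits for gaps of 0, 3 and 5 days.

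**How long a gap would remove the problem?** The deadline falls no later than the last session only if g is at least W − S, that is 28 − 6 = 22 to 31 − 4 = 27 days. It falls no later than the first session only if g is at least W, that is 28 to 31 days. Neither fits a scan taken immediately before treatment.

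**Does anything else force an earlier read?**
- Notification of a suspected lesion is immediate, but depends on a technician or team member noticing something. It does not bring the radiologist's read forward.
- The radiologist's oral report of an urgent finding follows the read, so it cannot speed it up.
- The PI and co-PIs decide inclusion (MRI Screening), and a research physician is present for safety (procedures for minimizing risks). Neither can act on a finding in a scan that has not been read.
- Participants may be removed for a change in medical status (Description of subject population). That power can be used only once the finding is known.

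The documents give no lesion frequency, MRI uptake or actual read times, so the number of patients affected and any harm cannot be estimated.

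**The case against.** The strongest reply is that imaging is not an eligibility test in this trial. The scans serve the mechanistic hypotheses, criterion 3 is ascertained by history and physician evaluation, and AH+ patients who decline MRI receive the same treatment unscanned. If an unsuspected lesion made tDCS unacceptable, every AH+ patient would need a scan. Laboratory results are a different case: they ascertain a listed exclusion and are drawn to establish treatment safety. One month is an outer limit, gross lesions are those staff are most likely to notice, and the protocol's risk section presents tDCS as low risk.

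Most of this stands, and it limits the size of the point. The laboratory rule shows only that this protocol can hold treatment for a result. It does not show that the protocol applied its own standard inconsistently. What remains is narrower: the scan is already held, a radiologist is already committed to reading it, and reading it sooner makes the result usable.

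Three stronger readings are tempting, and the documents do not support them.
- A reader might infer a breach of criterion 3. The criterion covers only a known lesion, so treating a patient whose lesion is not yet known breaks no rule.
- A reader might infer that all AH+ patients should be imaged. Nothing in the documents makes imaging a general safety requirement.
- A reader might infer that a reported lesion could not stop treatment, because Criteria for Early Discontinuation names only CGI thresholds and participant choice. The removal power for a change in medical status is permissive and does not mention MRI, but it exists. The optional open-label week follows the 3-month visit, by which time a baseline read due within one month is already available.

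**Conclusion.** The point holds as a modest, inexpensive safety improvement for AH+ patients in the MRI component. It is not a protocol error. As written, an on-time read can come after the whole blinded course: about 19 to 27 days after the last session with a gap of 0 to 3 days between scan and first session, or 8 to 13 days with a gap of 14 days.

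The figures rest on one month being 28 to 31 days and on an assumed gap. The attached Schedule of Events, which was not supplied, could fix the scan day. The direction does not depend on the exact choice, because only a gap of at least 22 to 27 days would bring the deadline back to the last session. These figures describe what the deadline permits, not when scans were actually read.

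The continuation application reports that all interventions are complete. The change can no longer protect these participants and is of use only to a later protocol built on this design.

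**What to change.** For AH+ patients in the MRI component, require the same radiologist to read the baseline structural scan before the first tDCS session, and before assignment to active or sham where possible. State that a structural lesion reported as clinically significant meets exclusion criterion 3. Keep the one-month window for post-treatment scans and for both comparison groups.

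Reading before assignment is preferable because an exclusion made then does not remove a randomised patient. The supplied SAP has no rule for post-randomisation exclusions.

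The cost is an expedited read, or a gap of a few days between scan and first session, which puts baseline imaging slightly further from treatment. MRI volunteers would face a slightly stricter check than AH+ patients who decline MRI, applied equally in both arms. No extra scan or reader is needed.

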The purpose of the present research is to test a potential new treatment for auditory verbal hallucinations in schizophrenia that uses transcranial Direct Current Stimulation (tDCS), a neurostimulation technique that passes an extremely weak electric current through the brain. During the treatment, two electrodes are positioned on the scalp above regions of the brain implicated in abnormal cortical activity associated with auditory verbal hallucinations in schizophrenia (1-3). Due to the directional flow of current, one electrode, termed “cathodal”, inhibits cortical activity, and the other, termed “anodal”, increases cortical activity. These electrodes will be placed such that cathodal stimulation is applied to an area associated with hyperactivity and anodal stimulation to an area associated with hypoactivity. One preliminary study has

revealed that this form of neurostimulation can alleviate auditory verbal hallucination symptoms both immediately following five days of treatment and up to three months after the final treatment(4). The goal of this study is to replicate these effects and explore the mechanisms that may underpin them.

45 patients with persistent auditory verbal hallucinations will be recruited to this study. Each individual will participate in behavioral assessments lasting up to 3 hours each and will then be randomized to receive a series of active vs. sham tDCS treatments. For active treatment, patients will have the inhibitory (cathodal) tDCS electrode placed over left auditory cortex relative to an anodal placed over frontal cortex on the right side. tDCS treatments will take place for 20 min per day for 5 consecutive days. For sham, procedures will be similar except that sham (inactive) tDCS treatment will be used. Assessment batteries will then be repeated following completion of treatment and at 1 and 3 mo following treatment. In addition, patients will be offered the possibility to participate in a concurrent magnetic resonance imaging (MRI) study aimed at evaluating the effects of tDCS on activation of auditory cortex during a auditory discrimination task as well as on other imaging parameters related to resting brain activity and metabolism. Patients who agree to participate in this MRI study will be scanned before and after active or sham tDCS.

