Since the development of tDCS in the 1960's, hundreds of subjects have participated in studies and received tDCS without any adverse effects. There has been no evidence of neuronal damage induced by tDCS: in two evaluations, Nitsche and colleagues (25, 26) found no elevation of neurone-specific enolase (sensitive marker of neuronal damage). McCreery et al.,(27) demonstrated that current densities below 25mA/cm² do not induce brain tissue damage even by applying high-frequency stimulation over several hours. In our protocol, we stimulate with a maximum current density of 0.057 mA/cm², a thousand fold below this limit. Duration of stimulation is an additional factor contributing to potential tissue damage, which has been detected at a minimum total charge of 216 C/cm² (28). (Total charge=current density x stimulation duration.) This protocol exposes subjects to maximum total charges of 0.022 C/cm², which is far below the established safety threshold. Iyer et al. (29) demonstrated the safety of tDCS applied at 1mA and 2mA for 20 minutes to normal subjects and noted some enhancement of verbal fluency after 2mA of stimulation, but no adverse events. A recent study (30) has demonstrated the safety of 1mA of cathodal tDCS for 20 min in patients with refractory epilepsy. The authors concluded that tDCS does not induce seizures and may have an anti-epileptic effect. Fregni et al, in May 2006 (31), report that patients suffering from central pain secondary to traumatic spinal cord injury safely tolerated tDCS at 2mA for 5 consecutive days, 20 min daily, with significant pain improvement but no significant influence on cognitive performance before and

after treatment.

Some participants reported redness, itching, and mild scabbing of the skin under the electrodes during and after tDCS. Some subjects have reported a sunburn like sensation under the electrodes while current was turned on. This has sometimes persisted for an hour or more after the current was turned off. Mild scabbing has also been observed under an electrode, which resolved after a few days. Both of these events (sunburn like sensation and scabbing) appear to be related to drying out of the sponge electrodes, which we learned from another investigator working with tDCS. Since then we have kept the sponges sufficiently moist, and irritation has been minimal or absent, while scabbing has not recurred.

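### The printed sham pulse setting (110 mA over 15 ms every 550 ms) contradicts the protocol's own account of sham and its stated maximum current density, and two sections describe the sham differently

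*Protocol*

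**What the plan says.** Four places in the protocol bear on what the sham arm receives.

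- **Study Procedures, Treatment.** For active stimulation, "the stimulation level will be set at 2 mA for 20 minutes". For sham, electrode positions are unchanged, "the same fade in/fade out ramp will be applied and the constant current will last only 30 s", and then: "Small current pulses will also occur infrequently (every 550 ms, 110 mA over 15 ms) through the remainder of the 20-minute session". The stated purpose of the pulses is to make the two conditions feel alike. The same section gives sponge electrodes of 7 x 5 cm.
- **Study Procedures, Overview (AH + Sample).** Here, under sham, "currents are initially ramped up over 30 s as in the active condition, but then immediately ramped down". This account mentions neither a plateau nor pulses. It goes on to say that, from prior experience, subjects cannot tell the two conditions apart.
- **Lay Summary.** For the comparison arm, "sham (inactive) tDCS treatment will be used".
- **Risks, tDCS (AH+ Sample Only).** The safety argument states that "we stimulate with a maximum current density of 0.057" mA/cm².

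The SAP gives no sham settings.

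**The concern.** The Treatment section calls the pulses small and infrequent, but the figures beside those words describe pulses far above the active current, recurring almost twice a second. Nor can those figures be squared with a sham labelled inactive, or with a maximum density that appears to be worked out from the active current alone.

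Hypotheses 1 to 4 in Specific Aims are each framed as active against sham, and the SAP's primary analysis takes group as its between-subjects factor. What that contrast means depends on what sham delivered. If the printed setting were followed, the comparator might not be inactive and would lie outside the protocol's own safety figure. If it is a misprint, the comparator may be exactly what was intended, but the protocol does not record it correctly.

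The second disagreement, between the Overview and Treatment, does not depend on the unit. The two sections differ on whether there is a constant-current phase. The statement that subjects cannot distinguish the conditions also sits beside the description without pulses, whereas Treatment relies on pulses to produce similar sensation.

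**Working it through.** **Inputs from the protocol.** Active current 2 mA for 20 min = 1200 s (Treatment). Electrode area 7 x 5 = 35 cm² (Treatment). Sham pulses 110 mA, 15 ms, every 550 ms, for the rest of the session (Treatment). Sham plateau 30 s (Treatment). Ramp-up 30 s (Overview). Maximum density 0.057 mA/cm² (Risks).

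**Assumptions, because the documents are silent.** 110 mA is the pulse amplitude. The sham plateau is at the active level of 2 mA. Each ramp counts as either 0 s or 30 s within the 20 minutes, with a mean of 1 mA while ramping. The 550 ms is either the full period or the gap between pulses (period 550 + 15 = 565 ms). Pulse shape and polarity are varied below.

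**1. Reproduce the stated maximum.** 2 mA / 35 cm² = 0.0571 mA/cm², which matches 0.057. The figure therefore covers the 2 mA current and nothing larger.

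**2. Pulse amplitude.** 110 / 2 = 55 times the active current. Peak density is 110 / 35 = 3.14 mA/cm², and 3.14 / 0.0571 = 55 times the stated maximum. This step does not depend on shape or polarity.

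**3. Pulse frequency.** 1 / 0.55 s = 1.8 per second. The remainder of the session is 1200 - 30 = 1170 s without ramps, or 1200 - 30 - 60 = 1110 s with two 30 s ramps. That gives 1170 / 0.55 = 2,127 or 1110 / 0.55 = 2,018 pulses.

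**4. Mean current during the pulse phase.** Mean = 110 x shape factor x 15 / period. For rectangular pulses, 110 x 15 / 550 = 3.00 mA, or 110 x 15 / 565 = 2.92 mA.

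**5. Session charge.** Active: 2 x 1200 = 2,400 mC without ramps, or 2,400 - 60 = 2,340 mC with them. Sham = mean pulse current x remaining time + plateau (2 x 30 = 60 mC) + ramps (0 or 60 mC). For rectangular pulses with a 550 ms period and no ramps, 3.00 x 1170 + 60 = 3,570 mC, and 3,570 / 2,400 = 1.49. At the other end (565 ms, 30 s ramps), the total is 3,362 mC, and 3,362 / 2,340 = 1.44.

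| Pulse shape, one polarity | Shape factor | Mean pulse current (mA) | Sham charge / active charge |
|---|---|---|---|
| Rectangular | 1 | 2.92 to 3.00 | 1.44 to 1.49 |
| Half-sine | 2/π | 1.86 to 1.91 | 0.93 to 0.96 |
| Triangular | 0.5 | 1.46 to 1.50 | 0.74 to 0.76 |

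With a 550 ms period, the pulse-phase mean exceeds 2 mA only if the shape factor is above 2 / 3.00 = 0.67. If polarity alternates, net current could be near zero whatever the shape.

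**6. If the unit were one thousandth as large.** 0.110 x 15 / 550 = 0.003 mA, and 0.003 / 2 = 0.15% of active. Over 1110 s the pulses would add 0.003 x 1110 = 3.3 mC, so the ramps and plateau would supply almost all of the sham charge.

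**7. Overview against Treatment, pulses left out, 30 s ramps.** Overview: two ramps = 60 mC, and 60 / 2,340 = 2.6% of active. Treatment: ramps plus plateau = 120 mC, and 120 / 2,340 = 5.1%. The two descriptions differ, but by little charge.

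**The case against.** The best reply is that nobody meant the printed amplitude. The words around it (small, inactive, pulses that serve only to mimic sensation) and the density figure all point to a slip in the unit, or to a prefix symbol misread when the PDF was turned into text. That is likely, and it is the main reason for not taking the printed figure as a description of what happened. It does not remove the point: nothing in the documents settles the unit, and the stated comparator runs from negligible to above active depending on it.

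Several stronger readings should be set aside.

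- A reader might infer that sham delivers more current than active. That needs rectangular pulses of one polarity, and the protocol states neither.
- A reader might infer that the approved density was exceeded in patients. Nothing shows that such a current was programmed or delivered. The documents show only that the stated maximum does not cover the sham pulse as printed.
- A reader might infer that a null result could not be interpreted. That would follow only if the verified sham charge turned out to be substantial.
- A reader might infer that the Overview describes a sham without pulses, and so without masking after the first minute. The Overview is a summary and is silent on pulses; it does not exclude them. The firm conflict there is an immediate ramp-down against 30 s of constant current, and step 7 shows that this alone is small.

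It is also true that the Application for Continuation records all interventions as complete, so a text correction cannot alter what was given. It can alter what is reported: the same section says that analysis continues and that a manuscript has been submitted.

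**Conclusion.** The point holds as a contradiction within the protocol. As printed, the sham pulse is 55 times the active current and 55 times the stated maximum density, against wording that calls the pulses small and the sham inactive. That part assumes only that 110 mA is the pulse amplitude.

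The size of any effect on the active-sham contrast is undetermined. At the printed unit, session charge is about 1.4 to 1.5 times active for rectangular one-polarity pulses and about 74 to 96% of active for half-sine or triangular ones, with a net near zero possible if polarity alternates. At one thousandth of the unit, the pulses are negligible. Separately, the Overview and Treatment disagree on the constant-current phase whatever the unit.

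The documents do not say which setting is right, and this review does not choose one.

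**What to change.** 1. Verify the sham amplitude and its unit, the pulse width, the interval and the plateau length against the device's programmed sham settings, and check the printed unit in the original document. Record pulse shape and polarity at the same time.
2. Reconcile the Lay Summary, Overview, Treatment and Risks (tDCS) sections to one sham description, and make sure the stated maximum current density covers both arms.
3. In the trial report, give the sham settings and the delivered sham charge as a fraction of active. Describe the contrast as something other than active against inactive sham only if the verified sham charge is not negligible.

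The cost is a check of device settings and a short correction to the text. No patients, procedures or reanalysis are needed. With a manuscript already submitted, the check should be made before the published methods repeat the unreconciled description.
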